### I. Research Objectives/Background

#### **Neuraminidase inhibition as a novel treatment to improve endothelial function in type 2 diabetes (T2D)**

The endothelial glycocalyx is a thin layer of interwoven glycoproteins and proteoglycans that forms a luminal mesh separating the vascular wall from the flow of blood. One of the glycocalyx's primary functions is to serve as a mechanosensor of shear stress in flow-mediated dilation (FMD). In this regard, our preliminary data, and published work by others, show that neuraminidase activity decreases the volume of the glycocalyx on the endothelial surface of arteries, and consequently impairs FMD responses. In this research project, we will determine the role that neuraminidase inhibition has on T2D-associated glycocalyx degradation and FMD impairment.

Currently, the only neuraminidase inhibitors approved for use in humans are those devised as influenza treatments. Therefore, they primarily target viral neuraminidases with IC50s in the nanomolar range. However, of the four FDA approved inhibitors, zanamivir has the highest IC50 for mammalian neuraminidases. In our preliminary experiments, we show that neuraminidase inhibition with zanamivir in cultured endothelial cells protects the glycocalyx from degradation.

Moreover, to test the in vivo effectiveness of neuraminidase inhibition with zanamivir on improving endothelial function in diabetes, we treated T2D mice with zanamivir for five days, which is the treatment regimen approved for influenza. Results indicate that treatment with zanamivir reduced plasma neuraminidase activity and improved endothelial function. On the basis of these exciting results, we are taking a fully translational approach and will determine the capacity of a five-day treatment with zanamivir to improve endothelial function in T2D human subjects in a clinical trial.

The **objective** is to determine if neuraminidase inhibition with zanamivir is efficacious as a therapeutic strategy to restore endothelial function in T2D patients.

Twenty subjects will complete five days of treatment with zanamivir. Baseline measurements will be taken before the initiation of treatment, as well as after the

conclusion of the treatment period (*i.e.*, a total of two assessment visits per subject). Assessment visits will include: vitals (such as blood pressure, heart rate), fasting blood work for plasma neuraminidase activity, plasma sialic acid, plasma glucose and plasma insulin, brachial artery FMD, and glycocalyx integrity assessment via Glycocheck.

## II. Drugs/Biologics/Devices

### **Drug treatment, dose, route and regimen:**

Subjects will be treated with 10mg zanamivir twice a day for five days (same dose currently FDA-approved for influenza treatment). Zanamivir will be administered via oral inhalation. [name], MD (co-investigator) and [name], MD (safety officer) will oversee the trial.

### **Rationale for choosing the drug and dose:**

As stated above, the proposed dose and administration route of zanamivir for this study are the same as the dose and administration route currently approved by the FDA for the treatment of influenza. Zanamivir was chosen from the four currently approved neuraminidase inhibitors because of its highest IC50 for mammalian neuraminidases.

### **Risks and safety information**

Per Relenza (zanamivir) packaging insert:

- Medication will not be administered in patients with a history of allergic reaction to any ingredients in the medication, including lactose (which contains milk proteins).
- Most common adverse events are: sinusitis, dizziness (in treatment studies) and fever and/or chills, arthralgia, and articular rheumatism (in prophylaxis studies). Zanamivir will not be administered until two weeks following administration of live attenuated influenza vaccine and the live attenuated influenza vaccine should not be given until 48 hours following cessation of zanamivir.
- Zanamivir also carries warnings/precautions for: bronchospasm, allergic reaction, neuropsychiatric events.

### **IND:**

An Investigational New Drug (IND) is not included as part of this protocol because the study medication, zanamivir is being used at an FDA approved dose in a population that is not anticipated to have increased risk or decreased acceptability of risk. Furthermore, individuals who have COPD or asthma will be excluded from the trial as these conditions may increase risk of adverse events. Lastly, no information will be submitted to the FDA to support a labeling indication, a labeling change, or a change in advertising, as this is not the intent of the current study.

### III. Recruitment Process

Patients with T2D (n=20) will be recruited from the MU Cosmopolitan Diabetes Center, MU Department of Medicine clinics, and the Columbia community by our research team. MU Health Care's electronic medical record has informatics tools and databases used for developing research studies, including i2b2 (Informatics for Integrating Biology and the Bedside) and RedCap (Research Electronic Data Capture). As in prior studies, with IRB approval, we contact patients and inform them of the potential to participate in this research.

#### **Recruitment:**

Subjects will be recruited from the University of Missouri-Columbia as well as the local community by [name] and our research team.

1. A chart review of clinic patients from the Division of Endocrinology, the Department of Medicine, and the Department of Medicine, and the Department of Family Medicine who are between the ages of 45 and 64 and have been diagnosed with type 2 diabetes will be completed in Powerchart by study coordinator/staff based on the study inclusion/exclusion criteria. A letter, chart message, or phone call will be utilized to notifying them of their eligibility to participate in a research study. Study coordinator/staff will work in conjunction with healthcare providers that have a direct patient care relationship to recruit subjects from clinics. If patients indicate an interest in the study after they are initially contacted by the study team, they will be sent a follow up email with a Qualtrics screening link and more details about the study.
2. Subjects may respond to the recruitment flyers, word of mouth, or advertisements posted in MU Hospital clinics, MU Hospital television screens, MU Info, or any place generally accessible to the public (i.e., grocery stores, community centers, newspapers, Facebook, etc.). Only recruitment materials approved by IRB will be posted. For all recruitment, subjects will be given an email address and/or a phone number to contact. After email or phone contact is established, subjects will be given a link to complete a screening questionnaire via Qualtrics: ([https://missouri.qualtrics.com/jfe/form/SV\\_2truBrLOYWemj3g](https://missouri.qualtrics.com/jfe/form/SV_2truBrLOYWemj3g)).
3. Subjects may also be identified and contacted via Studykik services. (Studykik will be provided with copies of IRB-approved recruitment materials to post)

### IV. Consent Process

#### **Preliminary screening**

As part of preliminary screening, all individuals who are interested in participating in the research study will be required to complete a screening questionnaire (via Qualtrics or phone) to determine preliminary eligibility before being scheduled for a study screening visit. These questions are for preliminary screening only and are not used as study data. Questions include queries about health history/habits, age, sex, height, weight, tobacco

use, medications/ supplements, over the counter medications use, illness, and chronic conditions. The study design is described in general terms to subjects, with mention of factors most likely to impact subject interest in participating. If the subject is considered to fulfill the inclusion/exclusion criteria, an appointment will be scheduled for a review of medical history and written consent.

### **Screening and Consenting Visit**

For all subjects, informed written consent will be obtained using HIPAA Research Description and Consent Forms approved by the MU IRB. The study physician will be available to answer any potential questions. During that process, the subject will be asked to describe, in their own words, what the study procedures will be like. They will be provided with the study details. Review of the consent form will occur with study personnel in a quiet, unhurried setting. Comprehension will be assessed by asking the subject to explain the study in their own words. Participants will have adequate opportunity to review the informed consent and to ask any questions they may have about the research protocol, compensation, risks, and benefits of taking part in the study. This study visit will also include collection of medical history and payment information and Glycocheck instruction and practice with the participant.

## **V. Inclusion/Exclusion Criteria**

### **Inclusion:**

1. Men and women with a BMI of 25-39 kg/m^2
2. Ages 45-64 years at randomization
3. Diagnosis of T2D based on physician diagnosis
4. No vulnerable populations (e.g., prisoners, pregnant, children) will be enrolled

### **Exclusion criteria:**

1. Cardiovascular disease including myocardial infarction, heart failure, coronary artery disease, stroke
2. History of chronic renal or hepatic disease
3. Active cancer
4. Autoimmune diseases
5. Immunosuppressant therapy
6. Hormone replacement therapy
7. Excessive alcohol consumption (>14 drinks/week for men, >7 drinks/week for women)
8. Current tobacco use
9. Pregnancy (premenopausal women will be required to complete a urine pregnancy test before participation)
10. History of asthma or chronic obstructive pulmonary disease
11. History of allergic reaction to lactose or milk proteins
12. Intranasal live attenuated influenza vaccine (LAIV) given within 2 weeks before zanamivir administration or a planned dose within 48 hours after zanamivir administration. Product insert states to avoid zanamivir administration with intranasal live attenuated influenza vaccine (LAIV).

## VI. Number of Subjects

The design for this clinical trial is a 5-day pharmaceutical treatment with pre- and post-assessment.

The clinical trial is powered to detect a 25% effect of zanamivir on FMD. Based on pilot data, this represents approximately one-third of the distance in mean response between healthy and T2D subjects. Our pilot data were also used to estimate the within-subject variance, assuming a correlation of  $r=0.6$  between serial measurements on the same subject (Harris, Padilla *et al.*, 2006). Sample size was estimated using the software package PASS and confirmed using code from Jones & Kenward (2015). A total size of 18 subjects will provide 80% power to detect a 25% difference when testing a two-sided alternative with alpha of 0.05. The final sample size will be increased to 20 to accommodate as much as a 10% drop-out rate. A  $p<0.05$  will be considered significant throughout all analyses.

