### **Changes to existing therapies**

For scientific purposes, it would be best to have patients who are not on medications; however, it would neither be safe nor ethical to completely discontinue medications. Therefore, we will study patients on their existing drug therapy but will limit recruitment to patients on the fewest medications. Common medications in T2D (*e.g.*, insulin, metformin, gliptins, GLP-1 analogs, SGLT2i, antihypertensives, antidepressants, statins) will be considered during recruitment, analyses (*e.g.*, using covariate analysis) and interpretation.

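### Does the plan need to say whether the unadjusted or the medication-adjusted FMD change decides the trial?

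*Combined protocol and SAP*

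**What the plan says.** The objective in Section I is to "determine if neuraminidase inhibition with zanamivir is efficacious as a therapeutic strategy to restore endothelial function in T2D patients". Section VI describes the design: "The design for this clinical trial is a 5-day pharmaceutical treatment with pre- and post-assessment". It names FMD as the outcome for which the trial is powered, takes the within-subject variance from pilot data, assumes a correlation of 0.6 between serial measurements, and states: "A total size of 18 subjects will provide 80% power to detect a 25% difference when testing a two-sided alternative with alpha of 0.05". Enrolment is 20, to allow for 10% drop-out. The section closes with the rule that p<0.05 "will be considered significant throughout all analyses".

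The section on changes to existing therapies explains why patients stay on their usual drugs. It says that the team "will limit recruitment to patients on the fewest medications" and that common drugs ("insulin, metformin, gliptins, GLP-1 analogs, SGLT2i, antihypertensives, antidepressants, statins) will be considered during recruitment, analyses", for example "using covariate analysis) and interpretation") will be taken into account. It gives no model, coding, list of covariates, or rank relative to the comparison in Section VI.

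**The concern.** The trial's conclusion rests on one pre/post comparison in about 18 evaluable subjects. If both an unadjusted and a drug-adjusted FMD result are produced, each is judged at p<0.05, and neither is named as decisive, two things could go wrong. The more favourable result could be chosen, which would raise the false-positive rate above 5%. Or a real effect could be reported as lost after adjustment, only because of how drug use was coded. With eight drug classes listed as examples and so few subjects, some adjusted models would be very imprecise.

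**Working it through.** **Inputs.** From Section VI: n = 18, power 80%, two-sided alpha 0.05, a 25% effect, r = 0.6, 10% drop-out. The documents give no SD for FMD and no frequency of drug use. Three classes, use of 15-50% each, and no true drug effect on the change are assumptions.

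**The plan's own figure.** Without the SD, 80% cannot be reproduced independently, so the standardised paired effect is solved from it. For a paired t-test with 17 df, 80% power needs a noncentrality of 2.973, so d = 2.973/√18 = 0.701. The implied SD of the change is 25%/0.701 = 35.7% of the baseline mean. The drop-out step holds: 18/0.9 = 20.

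**Four ways in which drug use could enter**

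1. *Main effect only, two-visit model.* A drug taken at both visits cancels from the within-subject change. In one simulated data set the visit estimate was 0.6228 (SE 0.2185) both with and without three drug terms. Power stays at 80%.

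2. *Predictor of the change, mean-centred.* The intercept is still the average change in the sample. Only degrees of freedom are lost (18 − 4 = 14). Noncentrality 2.973 on 14 df gives 78.9%. The verdict differs from the paired test in 3-4% of trials under the planned effect.

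3. *Predictor of the change, coded 0/1, intercept reported.* The intercept is now the change in patients on none of the drugs.
 - One class, 9 users and 9 non-users: noncentrality 0.701 × √9 = 2.10 on 16 df, power 51%. With 3 users and 15 non-users: 0.701 × √15 = 2.71, power 72%.
 - Three classes, balanced and independent, each with use p: the variance is multiplied by 1 + 3p/(1 − p). At p = 0.5 the factor is 4, the noncentrality is 0.701 × √(18/4) = 1.49 on 14 df, and power is 28%.
 - Three classes with randomly drawn drug use, average power: about 61% at 15% use, 53% at 20%, 42% at 30%, 26% at 50%, 11% at 80%.

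4. *Predictor of the change, users and non-users averaged at equal weight.* With 3 and 15 subjects the variance factor is (1/3 + 1/15)/4 = 0.10, the noncentrality is 0.701/√0.10 = 2.22, and power is 55%. With 9 and 9 it is 80%. With three classes it is 38-71%.

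**False positives if either of two tests may count** (n = 18, three classes, 50% use, simulated): 5.7% for paired or centred, 9.0% for paired or 0/1-coded. Over the assumed range of use the figures are 5-6% for the centred model and about 7-9% for the 0/1-coded or equal-weight model.

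**Reading.** The first two routes agree with the paired test almost everywhere. The other two depart from it because they estimate something else: a drug-free subgroup, or an average over an artificial half-and-half mix of users and non-users.

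**The case for a change.** The strongest case for a change is that the silence is real. 0/1 indicators are ordinary coding, centring is not automatic, and the text does not forbid reading an intercept or equally weighted means as the treatment effect. Under the planned effect and the assumed range of use, the 0/1-coded intercept with three classes would give a different verdict from the paired test in 21-56% of trials, and equal weighting in 13-46%. Two or three sentences would close the gap at no cost in subjects or visits.

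The silence stands, and so does the arithmetic. The step from there to a defect does not. The loss needs three choices that the plan does not make: drug-by-visit terms, uncentred coding, and a subgroup intercept presented as the effect of zanamivir. The low figures also depend on the number of classes and their frequency, which the plan does not give. 26% is neither a floor nor a property of the design, and the stated preference for patients on few drugs points to its higher end. The rule in Section VI sets a threshold for calling a result significant. It does not say that any one significant analysis settles the objective.

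Declaring the unadjusted test decisive also has a small cost. If three classes explained 30% of the variance in the change (an assumption), a centred model would have 91% power, and that gain would be given up.

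**Conclusion.** No change is called for. The plan leaves unwritten a rule that its own sample-size basis implies: a two-sided test of the within-subject FMD change, with within-subject variance and no covariates. The medication text explains why patients stay on treatment and offers covariate analysis as one example of taking drugs into account; it does not set up a rival deciding test. Adjustment is not needed to remove confounding either, because a drug that is unchanged between two visits days apart cannot bias the mean change.

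Under the paired test or either natural adjustment, power is 79-80%. The centred model with three classes disagrees with the paired test in 3-4% of trials, and letting either count gives 5-6% false positives. These figures rest on d = 0.701 solved from the plan's 80%, three classes, use of 15-50%, and no true drug effect on the change. The larger losses need an analysis that answers a different question from the stated objective. A sentence naming the paired comparison would only record what Section VI already implies.

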## VII. Study Procedures/ Design/Treatment Plan

### Assessment Visits

Subjects will complete two separate assessment visits over the course of five days. Pre-menopausal women will be required to complete a urine pregnancy test at both assessment visits, prior to the completion of other study activities. Subjects will undergo brachial artery FMD, Glycocheck, and blood chemistries taken at baseline testing. They will then complete a five-day treatment course with zanamivir. At the end of the treatment course, subjects will have all measurements repeated. Study procedures take approximately 3 hours to complete at each assessment.

### Special consideration in case of unforeseeable hardships such as public health emergencies or weather-related events

If subjects are not able to complete study visits, the following remedial steps will be taken:

1. Medication may be mailed to the subject through the investigational pharmacy.
2. In the case that subjects are unable to complete their follow up assessments at the originally scheduled dates, their medication course maybe delayed to better accommodate scheduling availability. Treatment duration will remain the same.
3. In the event of the Clinical Research Center (CRC) not being available or if it is considered by the study physician that performing studies there can be an increased risk of exposure to infectious agents or related hazards, the following alternative sites will be made available for screening, safety and study visits:
  - a. MUPAW, Diabetes Center.

These locations are not carpeted, and we do not anticipate an increased risk for the subjects given that medical supervision and nursing staff assistance will be unchanged.

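### Does the hardship provision leave the second assessment without a usable timing rule once dosing has begun?

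*Combined protocol and SAP*

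**What the plan says.** The Background section sets the aim, to "determine the capacity of a five-day treatment with zanamivir to improve endothelial function in T2D human subjects", and describes a baseline assessment plus one after treatment ends, "a total of two assessment visits per subject". Under Assessment Visits, section VII says "Subjects will complete two separate assessment visits over the course of five days" and then "At the end of the treatment course, subjects will have all measurements repeated".

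The hardship provisions that follow list three remedies:

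- Item 1: "Medication may be mailed to the subject through the investigational pharmacy".
- Item 2: "In the case that subjects are unable to complete their follow up assessments at the originally scheduled dates, their medication course maybe delayed", to suit scheduling, with the limit "Treatment duration will remain the same".
- Item 3: another location may be used for visits if the research centre is closed or judged hazardous.

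Section VI finds that 18 subjects give 80% power for a 25% difference in FMD, then adds: "The final sample size will be increased to 20 to accommodate as much as a 10% drop-out rate". Nothing in the protocol gives a tolerance in days around the second visit or says how a late measurement is analysed.

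**The concern.** Delaying a course is possible only before it starts. Hardships of the kind this section covers (weather, public health emergencies) can arise mid-course. Because the duration is fixed, the course cannot be stretched to meet a new visit date, and no pause is described. On that reading, a subject who misses the second visit after starting treatment is measured an unknown time off drug.

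The trial has no control arm, so the within-subject change in FMD is the whole result. Keeping a late value could dilute the mean change if the effect wears off. Leaving it out uses up the drop-out allowance. Everyone is treated and the Data Safety Monitoring Plan has the investigators following efficacy endpoints, so an unwritten keep-or-omit choice could be made with the results in view. A smaller question is whether the baseline still stands if the course is delayed after it was taken.

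**Working it through.** **1. Which cases are uncovered?**

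| When the hardship arises | Provision | Covered? |
|---|---|---|
| Before baseline | Item 2: the sequence can move together | Yes |
| After baseline, before first dose | Item 2: course can be delayed | Yes, but silent on whether the baseline stands |
| After first dose, research centre unavailable | Item 3: alternative site | Yes |
| After first dose, subject cannot attend either site | None | No |

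Only the last row can produce a late second visit. Its nominal time is still fixed, at the end of the course; what is missing is the tolerance.

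**2. The plan's own figure.** Inflating 18 for 10% drop-out: 18 / (1 − 0.10) = 20, as stated. The pilot mean and SD are not given, so the 80% power cannot be reproduced from inputs. I take it as true and back-solve a two-sided paired t-test at alpha 0.05. This gives a standardised change of 0.7007, so the SD of the change is 25 / 0.7007 = 35.7% of baseline.

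**3. Late values left out.** Power at a standardised change of 0.7007:

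| Pairs analysed | 20 | 19 | 18 | 16 |
|---|---|---|---|---|
| Power | 84.4% | 82.3% | 80.0% | 74.5% |

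**4. Late values kept.** The number late (k) and the share of effect remaining are assumptions, since the documents give neither. With none remaining, the mean change is 25 × (1 − k/20): 23.75% for k = 1 and 22.5% for k = 2. Power by simulation, 20 subjects:

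| Late subjects | None remains | Half | All | Left out |
|---|---|---|---|---|
| 1 | 80% | 82% | 84% | 82% |
| 2 | 75% | 80% | 84% | 80% |

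Keeping and omitting give the same power at about half the effect remaining. Below that, omitting is better; above it, keeping is better.

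**5. A harsher case.** With two ordinary drop-outs as well (18 pairs, two of them late, no effect remaining), keeping gives 68% and omitting (16 pairs) gives 75%.

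**6. Choosing after seeing results.** With the 25% effect present in on-time subjects, the two rules disagree on significance in about 5–6% of trials with one late subject and 8–10% with two. Under no effect, claiming success if either rule is significant raises the false-positive rate from 5% to about 6% (one late) or 6.5% (two). These are ceilings: they need both analyses to be run and the better one picked.

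**7. Older baseline.** The variance of a change is proportional to 2(1 − r): 0.8 at the plan's r = 0.6, and 1.4 if r fell to an assumed 0.3. For two such subjects in 20 the mean is (18 × 0.8 + 2 × 1.4) / 20 = 0.86. The standardised change becomes 0.7007 × √(0.8 / 0.86) = 0.676, and power 82% instead of 84%.

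**The case for a change.** The strongest case for acting is that the remedy is cheap and the choice cannot be repaired later. Writing a tolerance and one analysis sentence before enrolment costs almost nothing; once late values have been seen, nobody can show that the decision was independent of them. In a single-arm trial of 20, two subjects are a tenth of the data. The drop-out allowance is only two subjects, and the Compensation section's retention record (above 85%) does not promise that those places stay free for late visits.

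Much of this stands. The protocol has no tolerance and no rule for late values, and stating both would be good practice. Three parts are weaker. That the delay clause fails after dosing is an inference: the clause is permissive, does not say when it applies, and is coherent for conflicts known beforehand. The documents also do not supply the tolerance. Five days of visits in one place and assessment after treatment ends in another give no exact day, so any figure would be the reviewer's own. Finally, neither analysis rule can be called correct, because the ranking turns on how long an effect lasts, which the documents do not address.

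**Conclusion.** No change is called for. This is missing detail in a contingency clause, combined with a fair trade-off. The plan fixes when the second visit happens, and its hardship steps cover every case except a subject who cannot reach either site after the first dose of a five-day course. An analyst meeting such a case would ordinarily report the interval since the last dose and show the result with and without that subject.

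The size supports this. One or two late subjects among 20 leave power between 75% and 84%, against the planned 80%. It falls below 80% only if two are kept with less than about half the effect remaining, or if late visits coincide with ordinary drop-outs. Selective reporting would add at most about 1.5 percentage points to the false-positive rate. These results rest on the plan's 80% power at 18 being right, on assumed late counts and residual effects, and on a paired t-test. No document suggests that such cases are expected. How a course already begun should be handled is a clinical matter for the sponsor, and I take no view on it.
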